# 2.2.2.1.1 Clinical Studies

In the clinical studies conducted to date, a total of approximately 645 participants (including 265 DR-TB patients) have been exposed to Bedaquiline in the Phase 1 and 2 clinical trials conducted as a part of the development program for the treatment of MDR-TB. An additional 45 participants received Bedaquiline, either as monotherapy (B) or in combination with other agents (B-Pa or B-Z) in trial NC-001, and 45 more in trial NC-003 (B-Pa-Z, B-Pa-C, B-Pa-Z-C). In the Nix-TB (B-Pa-L) trial, 109 participants received Bedaquiline that led to an FDA approval in August 2019. Four shortterm Phase 2a trials enrolled treatment-naïve participants (C202, TMC207-CL001, NC-001 and NC-003). One long-term, open-label, Phase 2 trial, in MDR-TB participants (Bedaquiline- TiDP13-C209) and one long-term, Phase 2b trial, consisting of 2 different stages in participants infected with newly diagnosed sputum smear-positive pulmonary MDR-TB (Bedaquiline-TiDP13-C208), have been completed. Full details of the completed clinical studies are provided in the current bedaquiline IB, and Sirturo™ label.[8].

2.2.2.1.2 Safety

## Adverse Drug Reactions for Bedaquiline

Participants in the Any Bedaquiline group compared to the Any Placebo group (difference > 5.0%) had headache (23.5% versus 11.4%, respectively), nausea (35.3% versus 25.7%, respectively), arthralgia (29.4% versus 20.0%, respectively), and transaminases increased (6.9% versus 1.0%, respectively).and diarrhoea (11.4% versus 5.9%, respectively).

## Cardiovascular safety

During clinical studies with Bedaquiline a prolongation of QTc interval was observed. An ECG should be obtained prior to and after initiation of therapy with Bedaquiline to monitor the QTc interval.

Bedaquiline treatment initiation is not recommended in patients with:

- Heart failure
- QTcF interval > 450 ms (confirmed by repeat electrocardiogram)
- A personal or family history of congenital QT prolongation
- A history of or ongoing hypothyroidism
- A history of or ongoing bradyarrhythmia
- A history of TdP
- Concomitant administration of fluoroquinolone antibiotics that have a greater potential for significant QT prolongation (i.e., gatifloxacin, moxifloxacin and sparfloxacin)

Bedaquiline treatment must be discontinued if the patient develops clinically significant ventricular arrhythmia. An additive or synergistic effect on QT prolongation of Bedaquiline when co-administered with other medicinal products that prolong the QT interval cannot be excluded. Caution is recommended when using Bedaquiline concomitantly with medicinal products with a known risk of QT prolongation. If co-administration of such medicinal products with Bedaquiline is necessary, clinical monitoring including frequent ECG assessment is recommended.

In this trial, moxifloxacin will be co-administered with Bedaquiline. This is to prevent the development of resistance to the other drugs in the regimen in case the participant's strain of MTB

is resistant to pyrazinamide. ECG assessments will be performed on all participants at screening, baseline, and at treatment visits specified in the flow chart.

# Hepatic safety

Increases in transaminases were seen in clinical studies during administration of Bedaquiline with the background regimen. Participants should be monitored during treatment.

Other hepatotoxic medicinal products and alcohol should be avoided while taking Bedaquiline, especially in participants with diminished hepatic reserve.

# 2.2.2.2 Moxifloxacin [18, 19]

Moxifloxacin (M) is a microbial compound, approved in most countries around the world for the treatment of acute bacterial sinusitis, acute bacterial exacerbation of chronic bronchitis, community-acquired pneumonia, skin and soft tissue infections. Clinical studies have been carried out for many additional indications (urinary tract infections, pelvic infections, pharyngitis/tonsillitis, and tuberculosis). Moxifloxacin is an 8-methoxyquinolone whose oral formulation (which will be used in this trial) has enhanced activity against Gram-positive pathogens, and anaerobes while retaining useful activity against Gram-negative organisms. Moxifloxacin is not metabolized by or induces the cytochrome P450 system; thus, the risk of clinically relevant drug interactions is reduced. It has a positive safety profile within the fluoroquinolone class at the approved daily dose of 400 mg. **Moxifloxacin** while not approved for TB by most regulatory authorities, it is regularly used in second line MDR-TB treatment. The WHO TB Treatment Guidelines place moxifloxacin in the category of Group 3 drugs and notes that "all patients [with MDR-TB] should receive a Group 3 medication if the *Mtb* strain is susceptible or if the agent is thought to have efficacy. One of the higher generation fluoroquinolones, such as levofloxacin or moxifloxacin, is the fluoroquinolone of choice." It is currently in late stage clinical development for first-line TB treatment in combination with other TB drugs, including pyrazinamide in two different four-month long regimens.

Moxifloxacin is commonly used as second line therapy for TB (e.g., MDR- TB) and has also been evaluated in several clinical studies of participants with TB, including four 8-week treatment period Phase 2b studies.

In the usual daily doses of 400 mg/day, moxifloxacin is well tolerated. As stated in the Package Insert the most frequent individual drug related AEs observed in clinical trials with 400 mg oral moxifloxacin therapy were nausea (7.5%) and diarrhoea (5.8%). Fluoroquinolones, including moxifloxacin, are associated with an increased risk of tendinitis and tendon rupture in all ages.

A known but rare side effect of fluoroquinolones, including moxifloxacin is exacerbation of myasthenia gravis. In addition, moxifloxacin has been shown to prolong the QT interval of the electrocardiogram in some participants. It should be used with caution in participants being treated concomitantly with other drugs where an additive effect on the QT interval cannot be excluded.

Serious and sometimes fatal hypersensitivity reactions, including anaphylactic reactions, as well as peripheral neuropathy may occur after the first or subsequent doses of moxifloxacin. For additional information, refer to the moxifloxacin package insert.

For additional information on moxifloxacin, refer to the IB and the manufacturer's package insert.

# 2.2.2.3 Pyrazinamide

**Pyrazinamide** (Z) is a pyrazine analogue of nicotinamide and an approved anti-tuberculosis agent which is indicated for the initial treatment of active tuberculosis in adults and children when combined with other anti-tuberculosis agents and contributes significantly to the sterilization of lesions and thus treatment shortening.

Pyrazinamide (Z) is a standard drug used as part of the four drug HRZE regimen used for the first two months of intensive therapy for drug-sensitive TB as recommended by the WHO and many National TB programs. Z is active against TB *in vitro* and it potentiates the bactericidal and sterilizing activity of both Bedaquiline and pretomanid in mouse models of TB infection. Pyrazinamide enhanced the bactericidal activity of both Bedaquiline and pretomanid in Trial NC-001-(J-M-Pa-Z) as noted by decreases over 14 days in the CFU counts in sputum among participants.

The dose of pyrazinamide that will be used in this trial is an approved dosage for the treatment of TB. The most serious side-effect of pyrazinamide is hepatotoxicity and its frequency appear to be dose related. The pyrazinamide investigator brochure notes that pyrazinamide is contraindicated in persons with severe hepatic damage, who have shown hypersensitivity to it, and with acute gout. The most serious side effect is hepatotoxicity. Its frequency appears to be dose-related and thus liver function should be assessed before and regularly during treatment with pyrazinamide.

Hyperuricemia commonly occurs, occasionally accompanied by arthralgia, and may lead to attacks of gout. Photosensitivity and skin rash have been reported less frequently. Other side-effects that have been reported are anorexia, nausea and vomiting, malaise, fever, sideroblastic anaemia and dysuria. Pyrazinamide may decrease the efficacy of gout therapy (e.g., allopurinol, colchicine, probenecid or sulphinpyrazone) and dosage adjustments of these medications may be necessary. For additional information on pyrazinamide, refer to the investigator brochure.

# 2.3 Overall Benefit/Risk Assessment

The primary purpose of the Male Reproductive Safety – "BPaMZ/SEM"- clinical study is to evaluate the potential effect of pretomanid on human testicular function whilst being used in a 6-month antimicrobial combination regime. All participants in this trial will be given an antibiotic treatment regimen consisting of a 6-month Combination Treatment for Pulmonary Tuberculosis of Bedaquiline plus Pretomanid plus Moxifloxacin plus Pyrazinamide (BPaMZ). These drugs individually and in combination are not expected to have an adverse impact on Male Reproductive Safety, based on nonclinical and available clinical data. Similarly, these drugs individually and in combination are known to have anti-tuberculosis activity and is not expected to have an adverse impact on the ultimate cure of TB in these participants Based on NC-005 and other regimens using each of the regimen drugs in different combinations there is good evidence that this may be a highly effective therapy for both DS-TB and DR-TB. The same BPaMZ regime is also being studied in another ongoing clinical study NC-008 (the SimpliciTB study) This trial (SimpliciTB) will evaluate and support that, in additional to previous studies evaluated with BPaMZ, that this drug regimen (BPaMZ) will be safe and effective, is well-tolerated and could potentially shorten the current treatment duration compared to Standard HRZE/HR treatment for patients with drug sensitive TB

disease. This trial will also evaluate if this drug regimen (BPaMZ) given for 6 months will be safe and effective in drug resistant TB disease.

In addition to treating participant's pulmonary tuberculosis in the planned BPaMZ-SEM study we plan to assess the male reproductive safety profile of pretomanid with the same regimen (BPaMZ).

Participants in this trial will have their TB infection carefully characterized, with drug sensitivity profiles established, and they will receive treatment with trial drugs that have demonstrated activity against *Mtb*.

Participants will receive individualized medical attention; this will allow a continuous monitoring of the health conditions of each participant, any of whom can be withdrawn at any stage of the trial and removed from trial treatment should his/her condition suggest to the Investigator that this would be in his/her best interest. Multiple blood samples will be taken for safety laboratory studies, and ECGs will be taken at multiple time points.

The trial drugs in the proposed regimens to be tested in this trial have all demonstrated safety and efficacy in the treatment of pulmonary tuberculosis in non-clinical and clinical studies. Specifically, the regimen B-Pa-Z was generally well-tolerated and demonstrated bactericidal activity in a 14-day EBA trial. The potential risks associated with the trial drugs and regimens has been identified as outlined below and will be monitored carefully throughout the conduct of the trial.

One concern, the combination of two agents with known QT-prolonging effects (Bedaquiline and moxifloxacin), has been addressed specifically by carefully identifying and excluding participants with risk factors that might predispose them to cardiac arrhythmias, screening all participants for evidence of existing cardiac disease and monitoring all participants with ECGs throughout the trial.

The BPaMZ regimen is a novel regimen treatment expected to be effective, safe, and well-tolerated and might even shorten the current treatment duration for patients with TB. Based on data from previous trial evaluations of key monitoring and safety information as outlined suggests an overall favourable benefit-to-risk ratio.

# 3 Trial Objectives

# 3.1 Primary Objective:

To assess the male reproductive safety of pretomanid in the regimen (BPaMZ) of bedaquiline 200mg daily for 8 weeks then 100 mg daily for 18 weeks, together with pretomanid 200 mg (1x daily) + moxifloxacin 400 mg (1x daily) + pyrazinamide 1500 mg (1x daily) for 26 weeks in participants with Drug-resistant (DR) pulmonary TB.

## 3.2 Secondary Objective:

To evaluate the efficacy, safety and tolerability after 26 weeks of active treatment for TB and follow up for 52 weeks after start of the above-described treatment regimen in participants with Drug-resistant (DR) pulmonary TB.

TB Alliance Protocol Number: Pa-824-CL-012 Protocol Version: V4.0 07 APR 2022 Protocol Name: BPaMZ/SEM

# 4 Trial Endpoints

### 4.1 **Primary Endpoint**

• Change from baseline in total sperm count at 26 weeks.

### 4.2 Secondary Endpoints

- Change from baseline in total sperm count at 13 and 44 weeks.
- A key secondary endpoint will be the change from baseline in male reproductive hormones at Week 2, 4, 8,12,16, 26, 35, 44, 52, 65, 78, and at early withdrawal. Reproductive hormones: luteinizing hormone (LH), follicle-stimulating hormone (FSH), Inhibin B and testosterone.

### 4.3 Other Secondary Endpoints:

### Efficacy:

- Incidence of bacteriologic failure or relapse or clinical failure at 44 weeks after the start of therapy.
- Proportion of participants with sputum culture conversion to negative status in liquid culture (MGIT) at Week 4, 8, 12, 16, 22, 26, 35, 44, 52, 65, and 78.

### Safety and Tolerability:

- Change in weight from baseline.
- Incidence of Treatment Emergent Adverse Events (TEAEs) presented by incidence, severity, drug relatedness, seriousness, leading to early withdrawal, and leading to death.
- Quantitative and qualitative clinical safety laboratory measurements, including observed and change from baseline. Quantitative and qualitative electrocardiogram (ECG) results (heart rate, RR interval, PR interval, QRS interval, QT interval and QTc interval, including observed QT/QTc intervals and change from baseline) will be categorized.

### Pharmacokinetics (PK):

Plasma concentration of pretomanid from sparse sampling will be summarized as descriptive statistics.

## 5 Trial Design

## 5.1 Summary of Trial Design

This is a Phase 2, multi-center, open-label clinical trial in DR-TB in male participants aged 18 years and older.

The trial requires 20 evaluable and eligible male participants who meet all the inclusion criteria and none of the exclusion criteria diagnosed with DR-TB. All participants will receive the same regimen of BPaMZ once daily for 26 weeks. All participants must give written informed consent at screening visit (-21 day) to participate in this trial and continue with screening procedures during the screening period (Day -21 to Day -1).

## 5.2 Treatment Plan: Schedule of Assessments

- Screening Period (Day -21 to Day -1)
- Treatment Period (Day 1 to Week 26)
- Follow -up Period (Week 26 to Week 78)

Refer to:

- Trial Flow Chart (Section 1.1) for the timing of all procedures and laboratory samples to done at each visit.
- Trial Procedures (Section 8) for details regarding specific procedures or laboratory tests.

The Test Treatment Regimen, BPaMZ consists of a combination of the following products:

### Table 1: Products

Product	Tablet Strength	Abbreviation
Bedaquiline	100 mg	(B)
Pretomanid	200 mg	(Pa)
Moxifloxacin	400 mg	(M)
Pyrazinamide	500 mg	(Z)

Participants will receive Bedaquiline 200 mg once daily for 8 weeks then 100 mg once daily for 18 weeks, together with pretomanid 200 mg + moxifloxacin 400 mg + pyrazinamide 1500 mg once daily (BPaMZ) for 26 weeks.

Participants will enter post- treatment follow-up which continues until Week 78.

## 6 Trial Population

Participant must meet all inclusion and no exclusion criteria within the screening period. The screening period of -21 to -1 days provides flexibility for allowed retesting of applicable mycobacteriology, safety, or ECG parameters. Only one qualifying semen sample during screening is allowed within the -13 to -1 day period. Refer to Trial Flow Chart (Section 1.1) footnote f for further details. Sponsor may consider replacements of withdrawn participants.

## No protocol waivers will be granted by the TB Alliance

## 6.1 Inclusion Criteria

Participants are required to meet all the following inclusion criteria during the screening period to be enrolled. Patients must abstain from ejaculation for at least 2 days prior to screening clinic visit.

1. Understands study procedures and voluntarily provides written informed consent prior to the start of any study-specific procedures.

- 2. Male gender 18 years or over.
- 3. Body weight (in light clothing and no shoes)  $\ge$  45kg.
- 4. A positive molecular test for tuberculosis in sputum either at screening or within one month prior to enrollment.
- 5. Disease Characteristics:
  - Participants must have been diagnosed with TB prior to or at screening.
  - Participants' TB should be resistant to rifampicin and/or isoniazid (historical evidence of resistance to rifampicin and/or isoniazid is acceptable within 3 months prior to screening), and susceptible to fluoroquinolones by rapid sputum-based tests
  - Participants who have had previous treatment for DR-TB for more than 3 months at start of screening should be discussed with the medical monitor.
- 6. A chest x-ray, within 6 months prior to or at the screening visit, which in the opinion of the Investigator is compatible with pulmonary TB.
- 7. Participants will be required to use a double contraceptive method during the whole treatment duration and 18 weeks post dose.
- 8. Can comply with the protocol and the assessments therein, including all restrictions.

### 6.2 Exclusion Criteria

Participants will be excluded from participation if they meet any of the following criteria.

### Medical History and Concurrent Conditions:

- 1. Resistant to fluoroquinolones by rapid molecular test.
- 2. History of male infertility or vasectomy.
- 3. Unable to produce semen sample.
- 4. Evidence at screening of azoospermia.
- 5. Known erectile dysfunction that would prevent ejaculation.
- 6. Historical or active disease process of the male reproductive tract that would compromise sperm production. e.g., Tuberculous epididymitis.
- 7. History of any illness that, in the opinion of the Investigator, might confound the results of the study or poses an additional risk to the participant by their participation in the study.
- 8. Abuse of alcohol or illegal drugs that in the opinion of the Investigator would compromise the participants' safety or ability to follow through with all protocol-specified restrictions, visits, and evaluations.
- 9. Being, or about to be, treated for malaria.
- 10. Is critically ill and, in the judgment of the Investigator, has a diagnosis likely to result in death during the trial or the follow-up period.
- 11. TB meningitis or other forms of extrapulmonary tuberculosis with high risk of a poor outcome, or likely to require a longer course of therapy (such as TB of the bone or joint), as judged by the Investigator.

- 12. History of allergy or hypersensitivity to any of the trial IMP or related substances, including known allergy to any fluoroquinolone antibiotic, history of tendinopathy associated with quinolones.
- 13. For HIV infected participants any of the following:
  - a) CD4+ count <100 cells/µL
  - b) Received intravenous antifungal medication within the last 90 days
- 14. Participants with newly diagnosed tuberculosis and HIV that require initiation of appropriate HIV therapy before participants has received at least 2 weeks of an antituberculosis regimen.
- 15. Participants with any of the following at the Screening visit (per measurements and reading done by ECG):
  - a. QTcF interval on ECG >500 msec. Participants with QTcF > 450 must be discussed with the Sponsor Medical Monitor before enrollment.
  - b. Heart failure
  - c. A personal or family history of congenital QT prolongation
  - d. A history of or known, untreated, ongoing hypothyroidism, except for well treated hypothyroidism.
  - e. A history of or ongoing bradyarrhythmia
  - f. A history of Torsade de Pointe
- 16. Unstable Diabetes Mellitus which required hospitalization for hyper- or hypo-glycaemia within the past year prior to start of screening.
- 17. Receiving any form of hormone or hormone-like (nutraceuticals) therapy, except for well treated hypothyroidism.
- 18. Received Pretomanid and/or Delamanid to treat TB.
- 19. Known chronic hepatitis B or C.

## Previous and Concomitant Therapy

- 20. Use of any drug within 30 days prior to randomisation known to prolong QTc interval (including, but not limited to, amiodarone, amitriptyline, bepridil, chloroquine, chlorpromazine, cisapride, clarithromycin, disopyramide dofetilide, domperidone, droperidol, erythromycin, halofantrine, haloperidol, ibutilide, levomethadyl, mesoridazine, methadone, pentamidine, pimozide, procainamide, quinacrine, quinidine, sotalol, sparfloxacin, thioridazine).
- 21. For HIV infected participants:
  - a. The following antiretroviral therapy (ART) should not be used:
    - 1. Stavudine
    - 2. Zidovudine
    - 3. Didanosine
    - 4. Triple NRTI regimen is not considered optimal for HIV treatment (poor efficacy)
- b. A standard NRTI backbone may be combined with the following:
  - 1. Rilpivirine
  - 2. Dolutegravir
  - 3. Raltegravir
  - 4. Nevirapine
  - 5. Lopinavir/r
  - Participants who are on efavirenz, atazanavir/r or darunavir/r at the time of screening and have an undetectable viral load, should have their ART switched to one of the agents listed above (1-5). It would be preferable to switch to another permissible ARV within the same class accompanied by the same nucleoside backbone.
- c. ART regimen choice should be discussed with the Sponsor Medical Monitors if there are any concerns.

Confirmed plans to use Isoniazid prophylaxis for HIV positive participants during the treatment and follow up period is not permitted.

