### c. HIV Testing & CD4 Count

If HIV status is a confirmed known positive, a repeated HIV test is not needed provided that a documented HIV test result is available. If HIV status is unknown or suspected negative, a HIV test will be requested. If an ELISA and/or Western Blot and/or Electro-Chemiluminescence based HIV test was performed within 4 weeks prior to screening, it should not be repeated if documentation of testing method and negative HIV results can be provided. Repeated HIV testing during the Screening period is permitted for indeterminate HIV results.

CD4 count is required for HIV-positive participants.

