## 2.2.1.3 Pharmacokinetics

Important drivers of pharmacokinetic (PK) variability are dosing with or without food, and co-administration of medications that induce CYP3A4.

Bioavailability in the fasted state was about half that in the fed state, when administered at the clinical dose of 200 mg. Pretomanid should be administered in the fed state.

In the presence of rifampicin and efavirenz, pretomanid average concentration over a dosing interval (Cavg) was reduced 66% and 35%, respectively. Such strong and moderate CYP3A4 inducers should be avoided with pretomanid.

No clinically significant differences in the pharmacokinetics of pretomanid were observed based on sex, body weight, race (black, Caucasian, or other), pulmonary TB status, or human immunodeficiency status (HIV) status. The effect of renal or hepatic impairment on the pharmacokinetics of pretomanid is unknown.

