## 6.3 Restrictions

Concomitant medications should be kept to a minimum during the treatment period of the trial. However, if concomitant medications are necessary for the participant's welfare and are unlikely to interfere with the IMP, they may be given at the discretion of the Investigator. For any concomitant medications given as a treatment for a new condition or a worsening of an existing condition occurring after signing of the Informed Consent Form, the condition must be documented on the Adverse Event pages of the electronic Case Report Form (eCRF).

The prescribing information for all concomitant medication should be consulted and reviewed carefully. The determinations listed in the respective contraindicated, warning, and precaution sections must be respected to prevent any potentially serious and/or life-threatening drug interactions.

The following recommendations should be followed with regards to concomitant medication to avoid possible drug interaction with the IMP:

**Moxifloxacin**: The IMP should be taken either 4 hours before or 8 hours after taking the following products:

- An antacid, multivitamin, or other product that has magnesium, aluminium, iron, or zinc
- Sucralfate
- Didanosine

The following medicinal products are prohibited from the Screening visit and during the treatment period:

- Quinolone antimalarial (e.g., chloroquine and quinacrine). Participants who have malaria at screening are to be excluded. However, if a participant develops malaria during the trial, the Investigator is advised to consult the Malaria Treatment Guidance document regarding the interaction between moxifloxacin and bedaquiline with anti-malarial drugs. Investigators may also contact the Sponsor Medical Monitor for further guidance.
- Medicinal products used to treat pulmonary TB: including but not limited to gatifloxacin, amikacin, cycloserine, rifabutin, kanamycin, para-aminosalicylic acid, rifapentine, thioacetazone, capreomycin, other quinolones except moxifloxacin, thioamides, and metronidazole.

The following medicinal products should be avoided from Day 1 (Baseline visit) and during the treatment period as much as possible. Investigators may also contact the Sponsor Medical Monitor for further guidance.

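### Protocol Section 2.2.1.3 says strong and moderate CYP3A4 inducers should be avoided, but item 21 and Section 6.3 leave efavirenz ambiguous, and the semen summaries take no account of inducer co-medication

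*Protocol*

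**What the plan says.** **Protocol 2.2.1.3 (Pharmacokinetics)** gives the size of the interaction: "In the presence of rifampicin and efavirenz, pretomanid average concentration over a dosing interval (Cavg) was reduced 66% and 35%, respectively". It then says: "Such strong and moderate CYP3A4 inducers should be avoided with pretomanid".

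**Protocol 6.2, item 21** covers HIV-infected men.
- 21a, the list of antiretrovirals to keep out, names stavudine, zidovudine and didanosine and comments on triple-NRTI regimens. Efavirenz is not there.
- 21b opens with "A standard NRTI backbone may be combined with the following" and lists rilpivirine, dolutegravir, raltegravir, nevirapine and lopinavir/r. It continues: "Participants who are on efavirenz, atazanavir/r or darunavir/r at the time of screening and have an undetectable viral load, should have their ART switched", the target being one of those five.
- 21c refers concerns about the choice of ART to the Sponsor Medical Monitors.

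**Protocol 6.2, item 14** excludes men with newly diagnosed TB and HIV "that require initiation of appropriate HIV therapy before participants has received at least 2 weeks of an antituberculosis regimen". ART started later than that remains possible.

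**Protocol 1.1.1, flow chart and footnote c** provide for HIV status and, as the footnote puts it, "CD4 count is required for HIV-positive participants". Viral load is not in the flow chart, its footnotes, or the laboratory list in Section 8.3.

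**Protocol 6.3 (Restrictions)** says of medicines needed for the man's welfare that, if they "are unlikely to interfere with the IMP, they may be given at the discretion of the Investigator". It prohibits quinolone antimalarials and other pulmonary TB medicines. It asks that QTc-prolonging and hepatotoxic drugs be avoided as far as possible. Neither list names efavirenz or CYP3A4 inducers as a class.

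**SAP.** The ITT semen population (8.1.1) is everyone who took a dose. The per-protocol population (8.1.2) removes men without adequate treatment, which Section 7.3 defines by dose count, and men with major deviations (7.4). Section 9.1 summarises the primary outcome descriptively. Section 9.3 plots mean Week 2 to 26 trough against percentage change in total sperm count at Week 26.

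**The concern.** The trial asks whether pretomanid 200 mg daily harms sperm production. The protocol identifies a common type of co-medication that lowers pretomanid exposure and says to avoid it. The rules a site applies at screening and during treatment do not say this in one consistent way.

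If a man takes efavirenz through the 26 weeks, his sperm count reflects about two thirds of the intended exposure. An unchanged count from him is weaker evidence about the 200 mg dose than one from a fully exposed man, yet the semen summaries weight both alike. The direction of the distortion is predictable: towards no effect. The conclusion will rest on about 20 men, so each one counts.

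**Working it through.** **1. The plan's own figure.** 20 evaluable men with 20% dropout gives 20 / (1 − 0.20) = 25, which matches the enrolment target. No alpha, power, effect size or SD is stated, so there is nothing further to reproduce. The sample size does not bear on this point except as the denominator of 20.

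**2. The rules side by side.** Section 2.2.1.3 says to avoid the drug in every row below.

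| Situation | What the operative text says |
|---|---|
| Efavirenz at screening, viral load undetectable | 21b: switch |
| Efavirenz at screening, viral load detectable or unknown | No explicit instruction. 21a does not list it; the switch sentence does not reach it; it is outside the five agents in 21b |
| ART begun during treatment | Item 14 allows a later start. The switch sentence does not apply; the rest of item 21 carries no time limit |
| Rifampicin | Covered: 6.3 prohibits pulmonary TB medicines by an open-ended list that names rifabutin and rifapentine |
| Any other strong or moderate inducer | Not named as a class. Left to the general clause in 6.3 unless the drug stands on another list |

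The documented gap is therefore efavirenz (35%), plus any inducer that is neither a TB medicine nor otherwise listed.

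**3. Route through the SAP.** One dose puts the man in ITT. Adequate treatment is 146 of 182 doses (146/182 = 80.2%) within 182 + 56 = 238 days. It contains no exposure criterion, so full adherence on efavirenz passes. He leaves the per-protocol set only if he is classed as a major deviation, and item 21 does not make that clear.

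**4. Size.** Inputs: r = 0.35 (Protocol 2.2.1.3) and n = 20 (SAP 3). The documents give no number of affected men, k, so k is an assumption and is varied. Mean relative exposure = 1 − r·k/20. For illustration, assume a true 50% mean fall in sperm count at full exposure. If effect is proportional to exposure, the observed fall is 50 × (1 − r·k/20). If affected men show no effect at all, it is 50 × (1 − k/20).

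| k of 20 | Mean relative Cavg | Observed fall, proportional | Observed fall, no effect in affected men |
|---|---|---|---|
| 1 | 98.3% | 49.1% | 47.5% |
| 2 | 96.5% | 48.3% | 45.0% |
| 3 | 94.8% | 47.4% | 42.5% |
| 5 | 91.3% | 45.6% | 37.5% |

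The count of men with at least a 50% decrease (SAP 5, outcome 3) is more sensitive. Under proportionality, a man whose fall would be 50% at full exposure shows 50 × 0.65 = 32.5% and is not counted. One to three such men move that proportion by at most 1/20 = 5 to 3/20 = 15 percentage points.

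**The case against.** The case against has real weight.

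- **Item 21b may already exclude efavirenz.** It lists five partner drugs, efavirenz is not one, and the text describes the switch target as permissible. Read as a closed list, 21b does not allow efavirenz at all, and a man kept on it could be an entry-criteria deviation removed from the per-protocol set. This stands as one reading. The sentence that conditions the switch on viral load pulls the other way, because it gives no instruction for the remaining men.
- **General safeguards exist.** The non-interference clause, the instruction to consult the prescribing information of co-medication, and item 21c all apply. They rely on the site making the connection to Section 2.2.1.3.
- **Exposure is measured.** Pre-dose pretomanid is drawn at seven on-treatment visits, and SAP 9.3 plots mean trough against sperm-count change. Low exposure would be partly visible whatever its cause. This is the strongest point. But the plot leads to no listing or re-analysis. It also averages troughs over Weeks 2 to 26, which would blur a drug started midway.
- **The dilution is small** for one to three men, as the table shows.

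A reader might go further and infer four things that the documents do not support. First, that inducers are open across the whole 35% to 66% range: the 66% figure belongs to rifampicin, which the TB-medicine prohibition covers. Second, that efavirenz is plainly permitted: the text is ambiguous. Third, that an under-exposed man is formally scored as evidence of safety: the analysis is descriptive and has no pass threshold. Fourth, that all of item 21 applies only at screening: only the switch sentence is so limited. Nor is viral load necessarily unknown. The protocol does not schedule it, but a value may exist in HIV-care records.

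**Conclusion.** The concern holds as an inconsistency between the protocol's exposure warning and its operative rules, with a modest analytic consequence. Followed as written, the switch sentence leaves a man on efavirenz with a detectable or unknown viral load with no stated instruction, and the SAP would summarise his semen data without regard to exposure.

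The effect on the mean is minor: 98.3% to 94.8% of full cohort exposure for one to three men. An assumed 50% fall would appear as 49.1% to 47.4% under proportionality, or 47.5% to 42.5% in the extreme case. It becomes material only if several men are affected (37.5% in the extreme case with five). These figures assume 20 evaluable men, the protocol's 35% reduction lasting the whole treatment period, and a number of affected men that the documents do not supply. They would not hide a severe cohort-wide effect. The reasons to act are that the direction of bias is known, the cohort is small and the remedy is cheap.

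**What to change.** **Protocol.** Reconcile Section 2.2.1.3, items 14 and 21 of Section 6.2, and Section 6.3 so that they state one rule on inducer co-medication. The rule should cover men on efavirenz whose viral load is detectable or unknown, and ART started during treatment. If viral load stays in the rule, say where the value comes from. The sponsor's clinicians decide what the rule is; this review proposes none.

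**SAP.** Before database lock, fix the list of drugs that count as inducers, including at least those named in Section 2.2.1.3. List every man who took one during Weeks 0 to 26, using the concomitant-medication data already collected. Repeat the Week 26 total sperm count summary without those men as a sensitivity analysis, and read it beside the planned trough plot.

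**Cost.** Amendment wording and one extra table on a slightly smaller set. The SAP part is worthwhile even if enrolment has closed. If no man took an inducer, a one-line statement to that effect settles the matter.
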